### **Development of the intervention- Development of digital health messages**

In collaboration with the Tanzanian, German and American partners, we will develop the intervention that consists of digital health messages for the digital health education intervention, converting traditional learning material into a digital format such as a video, including sequences with interactive questions. When the enumerators and the doctoral research fellow are in the field, they will carry personal electronic devices; tablets. The tablet will contain both the videos and the digital questionnaires to be used in the surveys. The digital health messages will focus on public health important diseases in a Tanzanian context. The diseases have been selected after a need assessment locally, with the Tanzanian partners, and are diseases of public health importance. The digital health messages will address prevalence, causes / transmission, symptoms, treatment and prevention for HIV/AIDS, TB and TSCT. The local medical experts on the intervention diseases have pointed out key messages in traditional written material (some leaflets and some presentations), and the content is being reshaped and digitalized, before approval from the Ministry of Health Community Development, Gender, Elderly and Children (MoHCDGEC) in TZ will be sought to approve the health messages. The pedagogical strategy in the digital health messages is Micro-learning, applied to informal learning, which

enables users to learn without information overload, by the combination of micro-content with a sequence of micro-interactions. The micro-content will consist of the digital health message, and the micro-interactions will be the interactive questions that follow a key message. While developing the health messages, a constructive alignment approach is adopted, derived from the constructivist learning theory. This theory of learning can be summarized as following: First comes the key message – for example the health video that the client is watching on the device. Thereafter comes some digital questions, directly related to the key message. After the question is answered, the video continues. The outcome is presented first, and then the teaching and assessment are aligned to the outcomes. The learner's activities in creating meaning are central in this theory. The aim is that the digital health messages bring short important messages out to the target population, and that the clients can use this information to make good choices regarding own and family health.

In order to maintain the essential aim of the DigiI project, to give non-discriminating access to basic information, the digital health messages will also target the illiterate. Voice-over will be used, and the language will be Swahili. The viewers will not be asked about own health, rather their knowledge related to the intervention diseases. The questions in the videos will be the same questions as in the questionnaire.

### **Control group**

Participants from the control villages will serve as the control group and will be informed to live as normal. No restrictions or expectations will be given with respect to behavior change or information seeking, so they can continue the standardized care they get from the health information services.

### **Recruitment and participants**

The research population is people living in the selected villages, the study units are individuals, but only people over 15-70 years old are eligible for participating in the study. This is a two-stage cluster where the intervention villages initially were sampled by stratification, and two-stage sampling frame will be undertaken at a ten-cell and household level. The number of households within the ten-cells will be selected by the size of the ten-cell, according to the Probability Proportional to Size. In the randomly chosen households, 3-4 household members will be interviewed all together five times. Ten-cell and household lists will be used for randomisation in both groups.

A baseline survey conducted in both groups will determine the knowledge with regard to the diseases in the groups before the intervention is implemented.

In group 1, the random selected sample of people, previously naïve to health messages delivered by the DigiI project, will be given the intervention physically, as they will be shown the digital health messages at the researchers/ enumerators tablets. This is to make sure that all the participants in group 1 will actually receive the intervention, in order for the analysis to be able to indicate the overall effect of the digital health messages. All the participants in group 1 will be informed that the intervention is available for all, at all times, in the local Wi-Fi spot, however, we cannot be certain that the participants will use the intervention more than the first exposure by the enumerators.

Group 1 will, immediately after the exposure to the digital health messages, be asked the same questions as in the baseline questionnaire. 3 months, 6 months and 12 months after first exposure to the intervention, the questions will be repeated to the same participants.

Inclusion criteria:

- Living in the selected household (15-70 years), at least for the past six months, and at least planning to not move the next 12 months.
- Must be capable and willing to sign written informed consent and thumb-print for illiterate participants

Exclusion criteria

- Planning to be out of the village for more than 6 weeks in the next 12 months
- Those above 71 or under 15
- Not capable of signing consent letter (very sick)

In order to financially conduct the study, a cluster design is chosen over an individually randomised sampling procedure. The research group will be in contact with the participants five times, and it would demand increased financial resources if all ten-cells in the villages would be included. Even if the villages are not overwhelming in size, the populations are spread out over large areas.

To reduce contamination between intervention and control participants, the villages in the intervention and control groups are located at different geographical locations.

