**Last updated: 2.1.2019**

## Project summary

Increased health education has the potential to facilitate better use of health care services and to promote early treatment, thus it can strengthen the health care system, and ultimately reduce morbidity and mortality. In this study, we will develop and test the effect of digital health messages related to HIV, Tuberculosis (TB) and *Taenia solium* cysticercosis/taeniosis (TSCT) (the intervention diseases) in Migoli and Izazi (the intervention villages), in Iringa, Tanzania (TZ).

The intervention is planned as follows: A digital platform, providing the intervention villages with digital health messages related to the above-mentioned diseases, will be implemented in TZ in 2019. The platform will be accessible free of charge, through own devices and tablets based in the local Wi-Fi spots in the villages.

In the first part of the PhD-project, the doctoral research fellow will participate in developing the digital health messages, together with experts from the medical and teaching environments in Tanzania, Norway, Germany and USA.

The second part of the PhD-project consists of a cluster non-randomised controlled trial and semi-structured interviews in Tanzania. The digital health messages will be physically shown to the participants in the intervention group. The study is planned to investigate the knowledge related to the intervention diseases, before the intervention, immediately after exposure to the intervention, and at follow-up points throughout one year, after the intervention has been implemented. Semi-structured interviews with clients (users of the intervention) from each of the intervention villages are included, to explore the perception and reception of the intervention.

The baseline study and the immediate after survey will take place in Tanzania in Q1 2019, while the other follow-up studies and interviews (3, 6 and 12 months after baseline) will be undertaken throughout one year.

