## **WP 2 –A cluster non-randomised controlled trial**

The overall strategy chosen is a non-randomised controlled trial, with a two-stage cluster sampling. The study will be conducted in four villages in Iringa district in Tanzania, assessing the effect of digital health messages related to HIV / AIDS, Tuberculosis (TB) and *Taenia solium* cysticercosis/taeniosis (TSCT).

The aim of the digital health intervention is to contribute to increased health knowledge of the clients that has the potential to facilitate better use of health care services, and to promote early treatment, thus to strengthen the health system.

Hypotheses: We hypothesize that the intervention increases the proportion of correct answers, related to the intervention diseases, when comparing pre and post knowledge scores, also among clients that cannot read.

We will measure if the intervention leads to an increase in the number of correctly answered questions, from 21 out of 42, to 28 out of 42 (equivalent to 16,7 % increase) questions from the study questionnaire, during the 12-months intervention in the intervention group compared to the control group.

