### **Methods and study design**

Iringa district was selected because the prevalence of all three diseases is high, and the areas are known to be endemic, in addition to being a rural district with mainly unconnected villages. The intervention villages were conveniently chosen at an early stage in the DigI project, thus randomization of the participants to intervention / control groups will not be feasible. The intervention group, group 1, consists of randomly selected participants from the villages Izazi and Migoli.

Izazi village is not connected to internet, while Migoli has recently been connected through 3G. According to the village authorities, 3G is not used for health information.

The control group, group 2, consists of randomly selected participants from the villages Kimande and Idodi. These villages are candidates for the 7 next villages to get access to the digital health platform, in the DigI project phase II. The control villages are both located at least 70 km away from the intervention villages, and have at least three villages in between, in order to hinder contamination between the two groups.

Around 494 participants (15-70 years of age) will be included in the study. The study will take place at randomly selected households in the four villages. The ten-cells (sub-villages with up to 50 households) will be the clusters and randomization will occur at ten-cell and household level. Group 1 will receive a 12- months intervention, and group 2 will function as a control group and will get usual information through the village health posts available resources (see the section on control group below). Study variables will be measured at baseline, immediately after exposure to the intervention, 3, 6 and 12 months after exposure. The main outcome will be knowledge uptake and score after intervention, and scores related to retention of knowledge throughout the year.

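### The immediate post-exposure questionnaire is assigned to group 1 only, so the immediate knowledge change is an uncontrolled pre-post result and should not carry the effect claim on uptake

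*Combined protocol and SAP*

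**What the plan says.** All references are to the combined protocol and SAP.

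**Who is measured when.** Recruitment and participants covers both groups at the start: "A baseline survey conducted in both groups will determine the knowledge with regard to the diseases in the groups before the intervention is implemented". For the next round it names one group: "Group 1 will, immediately after the exposure to the digital health messages, be asked the same questions as in the baseline questionnaire". Study tools agrees, placing the immediate questionnaire in the intervention villages after the messages are shown to group 1. For controls, the Control group section says "Participants from the control villages will serve as the control group and will be informed to live as normal" and mentions no measurement.

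**Schedules that name no group.** Methods and study design: "Study variables will be measured at baseline, immediately after exposure to the intervention, 3, 6 and 12 months after exposure". Project summary: "The baseline study and the immediate after survey will take place in Tanzania in Q1 2019". That section counts the later rounds, at 3, 6 and 12 months, from baseline. Recruitment and participants also counts five interviews per household member and, near its end, five contacts per participant, again without naming a group.

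**What is to be concluded.** The first WP 2 objective is to assess the effect on uptake and retention from scores before and after, in both groups. The hypothesis in the WP 2 section rests on pre and post scores and names no control. The target that follows it, 21 to 28 correct answers out of 42, is set "during the 12-months intervention in the intervention group compared to the control group". Methods and study design then says: "The main outcome will be knowledge uptake and score after intervention, and scores related to retention of knowledge throughout the year". No visit is attached to uptake. The analysis section plans multilevel models and a comparison between intervention and control groups, also without naming a visit.

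**What the items are.** The section on developing the messages says that the questions asked inside the videos are those of the study questionnaire.

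**The concern.** Retention is listed separately as scores through the year, so the natural visit for uptake is the immediate one. As described, that is the one visit with no control data. A rise from baseline to the immediate questionnaire would be a within-group change on items that group 1 answered at baseline and met again in the videos. It could reflect lasting learning, familiarity from being asked again, or both, and nothing in the described data separates them.

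At stake is what the trial can conclude. Followed as written, the plan allows an immediate rise to be reported as the effect on uptake, within the main outcome. It contains a controlled comparison that is better placed to support an effect claim, but it does not say that the conclusion rests on it.

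**Working it through.** **Step 1. Assigning texts against unassigned texts**

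| Section | Immediate round | Group named |
|---|---|---|
| Recruitment and participants | asked after exposure | group 1 |
| Study tools | after the messages are shown | intervention villages |
| Project summary | same quarter as baseline | none |
| Methods and study design | listed in the schedule | none |
| Recruitment and participants | five interviews, five contacts | none |

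Both texts that assign the round give it to the intervention side. None gives it to group 2.

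**Step 2. Count the rounds**

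- Group 1: baseline, immediate, 3, 6, 12 months = 5.
- Group 2, if followed at 3, 6 and 12 months: baseline, 3, 6, 12 months = 4.
- Group sizes from Table 2: 195 + 52 = 247 intervention; 135 + 112 = 247 control.
- Planned interviews with 5 and 4 rounds: 247 × 5 + 247 × 4 = 1,235 + 988 = 2,223.
- Planned interviews if five applies to everyone: 494 × 5 = 2,470.
- Difference: 2,470 − 2,223 = 247, one full control round.

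The count of five therefore fits the assigning texts only if it describes group 1. If it covers controls, it conflicts with them.

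**Step 3. Earlier administrations of the questionnaire at each visit, on the 5 and 4 reading**

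| Visit | Group 1 | Group 2 |
|---|---|---|
| Immediate | 1 | not measured |
| 3 months | 2 | 1 |
| 6 months | 3 | 2 |
| 12 months | 4 | 3 |

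Group 1 is one administration ahead at every later visit and has also met the items in the videos. The extra questionnaire is a research procedure, while the in-video questions are part of the intervention; both add familiarity with the items. So 1 of the 4 post-exposure points has no described control. The other 3 can be controlled, but re-asking is unequal.

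**Step 4. Which contrast was the study sized for?**

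Inputs: p1 = 21/42 = 0.500; p2 = 28/42 = 0.667; power 80%; drop-out 20%; the figure 1,5 in Sample size calculation, read as a design multiplier. Two-sided alpha of 5% is an assumption, since the text available refers to an appendix for the calculation.

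Pooled-variance formula, per group, with mean proportion p = 0.583 and q = 1 − p:

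n = [1.960 × √(2pq) + 0.842 × √(p1q1 + p2q2)]² / (p2 − p1)²

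- √(2 × 0.583 × 0.417) = 0.697 and √(0.250 + 0.222) = 0.687.
- n = (1.367 + 0.578)² / 0.1667² = 136.2 (unrounded inputs), rounded up to 137.
- 137 × 1.5 = 205.5; 205.5 × 1.2 = 246.6, rounded up to 247 per group; 2 × 247 = 494.

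This matches Table 2 exactly. It shows that the study was sized as a two-group comparison. It does not identify the visit, and it does not show that the calculation is adequate.

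**The case against.** The strongest reply is that the plan is already comparative. The WP 2 objective asks for scores in both groups, the 21-to-28 target is set against the control group, the analysis section plans that comparison, and no section says that the immediate change alone will support an effect claim. All of this stands. A reader might infer that the trial as a whole is uncontrolled or that the sponsor means to rest its conclusion on the immediate rise; the documents support neither. But none of these texts names a visit for uptake, and the objective's promise of both groups is not met at the immediate visit as described.

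A second reply is that five interviews, stated without a group, may include controls. That too stands in part. A reader might take the missing control round as settled. It is the likelier reading, because two explicit assignments outweigh an unassigned count, but the texts conflict.

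Third, the time origin is a small matter: the Project summary counts follow-up from baseline and other sections count from exposure, yet it puts baseline and the immediate survey in the same quarter. For group 1 the gap may be short. For controls, who have no exposure date, the origin is undefined, so it belongs in the schedule. On its own it would be only missing detail.

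**Conclusion.** The point holds and should be fixed; confidence is moderate. As described, the immediate change is an uncontrolled within-group result and cannot by itself support a claim of effect on uptake. It directly concerns 1 of 4 post-exposure points. The documents give no retest gain, so the bias cannot be sized.

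Two stronger inferences should be resisted.

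- A reader might conclude that the weakness stops at the immediate visit and that the later contrasts are clean. They are not: group 1 would be one administration ahead at 3, 6 and 12 months and has seen the items in the videos, and Methods and study design says that the villages were chosen by convenience, so the groups are not randomised.
- A reader might take the WP 2 target as naming 12 months as the primary visit. It refers to the 12-month intervention period and compares with control; it does not designate a visit.

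The conclusion assumes that the two assigning texts govern over the unassigned count of five, and that controls are followed at 3, 6 and 12 months. The planned comparison with control implies follow-up of controls, but no section states those visits for them outright. The sample-size check rests on the assumed alpha and on reading 1,5 as a multiplier; the main finding does not depend on it.

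**What to change.** 1. In Main objectives in WP 2, the WP 2 hypothesis and target, and Methods and study design, label the immediate change as a descriptive within-group result in group 1.
2. State that the effect claim rests on the between-group difference in change from baseline. I propose 12 months as the main contrast, because it is consistent with the target set against the control group, with 3 and 6 months as supporting contrasts.
3. State as a limitation that group 1 has had more prior administrations of the questions than controls at those visits.
4. Give a schedule for each group. It should state that controls are measured at 3, 6 and 12 months and from which date these are counted. Reconcile it with the five interviews and contacts in Recruitment and participants and with the schedules in Project summary and Methods and study design. If a fifth control interview is intended, say when.

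These are text changes with no new data collection. The cost is that immediate uptake alone no longer supports a causal claim, and that an order is set among outcomes that Methods and study design lists without one.

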**Data collection and instruments**

The research team will have training prior to fieldwork. The doctoral research fellow will be in charge of training with regards to use of tablets, interviewing the participants, submission of digital questionnaires and uploading of the personal identification code (described below). The training will take place in Morogoro, at SUA.

**Study tools**

Enumerators from SUA and NIMR and the doctoral research fellow will collect the data in the field. The first round will consist of localizing the participants and the baseline study. Health message provision to participants in group 1, and the immediate after questionnaire, will follow in the intervention villages. The survey will start in Migoli, then Izazi, and then continue to the control villages, Kimande and Idoli. The first follow-up will start three months after exposure to the intervention, the second will start six months after, and the final follow-up will start 12 months after expose to the intervention.

When collecting the data through the questionnaire, an android app, KoboCollect, will be used. The questionnaire has been developed in KoboToolbox, a software for field data collection in challenging environments, developed by Harvard Humanitarian Initiative. This is a free, open source tool that allows their users to create and employ questionnaires, to be used in the field without Wi-Fi, 4G, 3G or other connectivity to internet.

Accessing KoboToolbox can only be done with username and password. The questionnaire will be shared with other users, the enumerators, who only will be able to submit data, but not access the collected information. When tablets are online the app will automatically synchronize the collected data to the online platform, KoboToolbox. After each survey round the information will be transferred from KoboToolbox to UiO’s Services for sensitive data (TSD) and a server at NIMR, and deleted from KoboToolbox. This is described further below. The digital questionnaire contains questions to be checked off at the tablet. The language in both the digital health messages and the questionnaire will be Swahili. In the first survey round, the participant will be asked about demographic information. This personal information; name, sex, age, mobile number, village and GPS coordinates, will be registered on the household list, and not in KoboCollect, nor uploaded to KoboToolbox, in order to reduce privacy information risk. A Digital Object Identifier (DOI) will be created to each participant, and the DOI will be registered in KoboCollect together with age segment and sex. Thus, no personal information will be uploaded to KoboToolbox. The personal identification key will be stored directly in TSD via the tablets, and will not be sent through email.

Tools to be used in the field	
A personal device, the tablet, containing:	Household lists, containing:

 
• A digital questionnaire (KoboCollect) with:               
 
1. DOI, Age segment, sex
 
2. 14 knowledge questions on HIV / AIDS
 
3. 11 knowledge questions on TB
 
4. 17 knowledge questions on TSCT
 
5. 5 questions on digital literacy
 
6. 6 questions on general health literacy
 
 
 
• Digital health messages.
 
	
 
• The personal identification key (household lists) with:               
 
1. DOI
 
2. Name
 
3. Sex
 
4. Age
 
5. Village
 
6. Mobile number
 
7. GPS-coordinates
 
 
 

Table 1

The reason for asking the participants for their names, mobile number and GPS is to be able to re-locate the participants in the follow-up surveys. In the follow-ups, the research staff will carry lists with GPS-coordinates,

together with names and DOIs. When entering the data from the follow-ups, the enumerators will only have to identify the participants according to the list, and use the DOI when collecting data.

In the follow-ups, the participants will be asked if they have used the intervention, at the local Wi-Fi spot, and if yes, how many times in the previous (three/six) months. This will provide information on the actual use of the intervention.

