The digital health messages will be accessible at a Wi-Fi spot in the local village close to the local health post. The digital health messages will also be shown face-to-face to each of the participants in the intervention group, by enumerators in the research team from SUA and the doctoral research fellow. The intervention will be available for all clients in the intervention villages, not only for the participants in the study described in this protocol.

The intervention will be maintained by NIMR Muhimbili Centre in Dar es Salaam during the first phase, but is going to be managed as a sustainable business model where a local sales man or woman is selling vouchers to access the World Wide Web. NIMR have close contact with the village authorities and health workers in the intervention villages, and will be alerted if the intervention for some reason is not functioning. The Wi-Fi network that provides the access to the digital health education platform, reaches within a radius of 50 meters, and is driven by a solar panel. This means that the intervention will be accessible even if the electricity locally shuts down.

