**Data management and statistical analysis**

A data management plan is being developed using a tool from the Norwegian Centre for Research Data (NSD). UiO is responsible for the data stored in TSD. The de-identification code will be stored separately in TSD, and deleted in 2022. After this, the anonymous data will be kept in NSDs archives, for re-use purposes.

The data will be analysed in TSD, by multilevel models to address the dependency related to cluster trials. Summary tables with calculated averages (mean, median, and mode), will be created. The baseline knowledge scores will be calculated with data from the first survey. The doctoral research fellow will compute an overall score for each section (prevalence, cause/transmission, symptoms, treatment and prevention) at individual and village level, based on the answers to the questions. Then a comparison between intervention groups and between intervention and control groups will be made. Data from the follow-ups will also be analysed in TSD accordingly.

After data collection is completed the GPS data will be able to illustrate the use of the intervention, related to distance from household to Wi-Fi spot and frequency of use. In this planned illustration, no direct households will be identified, but rather summarize on village level the frequency of the use of the intervention.

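### Staff who show the videos to group 1 are also named as outcome interviewers, and nothing keeps the two roles apart, so bias may favour the intervention after exposure

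*Combined protocol and SAP*

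**What the plan says.** **Showing the videos.** The Introduction has the messages shown face to face to each group 1 participant "by enumerators in the research team from SUA and the doctoral research fellow".

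**Collecting the outcome.** Study tools states: "Enumerators from SUA and NIMR and the doctoral research fellow will collect the data in the field". NIMR enumerators appear here but are not named as showing the messages.

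**Device and questions.** The section on development of the intervention says: "The tablet will contain both the videos and the digital questionnaires to be used in the surveys". The same section adds that the interactive questions in the videos are those of the questionnaire.

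**Timing.** Under Recruitment and participants, group 1 will "immediately after the exposure to the digital health messages, be asked the same questions as in the baseline questionnaire". The questions are then repeated to the same people at 3, 6 and 12 months.

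**The fellow's other roles.** The Project summary says "the doctoral research fellow will participate in developing the digital health messages". Data collection and instruments says: "The doctoral research fellow will be in charge of training with regards to use of tablets, interviewing the participants". Data management and statistical analysis says: "The doctoral research fellow will compute an overall score for each section".

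**Safeguards described.** Interviewers are trained before fieldwork, answers are ticked on a tablet, and enumerators can submit data but not see what has been collected. The text describes no separate assessors, no rule against prompting and no repeat-interview check. Table 1 lists no interviewer code among the contents of the form.

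**The concern.** The outcome is a knowledge score obtained by interview. If the person who has just taken a participant through the material also puts the questions, that person knows which answers were taught and has a natural interest in hearing them. A hint, a repeated question or a reminder of the video can raise the score without any gain in unaided knowledge.

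Control participants are told to live as normal and are not taught by the survey team, so this relationship has no counterpart in group 2. It also begins after baseline, so adjusting for baseline does not remove it. The main comparison could then credit the messages with some of what the interviewer contributed. The fellow's position deserves particular care, because that role combines helping to develop the messages, showing them, training interviewers and collecting the data.

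**Working it through.** The plan gives no figure for interviewer effects, so there is none to reproduce. The check sets the sections side by side and then asks which part of an interviewer effect would survive the planned comparison.

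**1. Overlap of roles**

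| Staff | Named as showing videos (Introduction) | Named as collecting data (Study tools) |
|---|---|---|
| SUA enumerators | yes | yes |
| Doctoral research fellow | yes | yes |
| NIMR enumerators | no | yes |

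Both groups of staff who deliver the intervention also collect the outcome. The overlap is documented by team. No section assigns interviewers to participants, so overlap for individual participants is permitted but not stated.

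**2. Opportunity.** Videos and questionnaire share a tablet, the questions are the same, and the first re-test follows the viewing directly. One staff member showing and then asking is a natural way to run this visit, and no sentence rules it out.

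**3. What cancels and what does not.** Write the observed mean score in group *g* at round *t* as

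observed(*g*, *t*) = true(*g*, *t*) + *c*(*t*) + *d*(*t*),

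where *c*(*t*) is the interviewers' general tendency, assumed common to both groups, and *d*(*t*) is the extra effect of being tested by one's teacher. *d*(*t*) is zero at baseline and zero in group 2.

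- Change in group 1: true change + *c*(*t*) − *c*(0) + *d*(*t*).
- Change in group 2: true change + *c*(*t*) − *c*(0).
- Difference in changes: true effect + *d*(*t*).

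General leniency therefore drops out if the same mix of interviewers serves both groups, which the plan does not specify. The term *d*(*t*) stays. It does not depend on the number of participants, so enlarging the sample of 494 would leave it unchanged.

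**4. Where *d*(*t*) is most likely.** The immediate re-test is the most exposed round, because teaching and testing fall in one visit. Recruitment and participants describes that re-test for group 1 only. If the result is read as a before-and-after change within group 1, *d* enters it in full. At 3, 6 and 12 months the same pairing of teacher and participant is still possible, but the mechanism is weaker.

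**5. Effect of the check-off format.** Ticked answers reduce the room for accepting a near-miss as correct. They do not affect what the interviewer says before the tick.

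**The case against.** The case against has real force, and most of it narrows the point.

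- **Team overlap is not individual overlap.** This stands. The documents do not show that anyone will test a participant whom they taught, and NIMR enumerators are not named as showing the videos.
- **One survey operation covers both groups.** This stands for general leniency or familiarity, which can arise in either group and largely cancels in change scores. It does not cover the teacher-tester part.
- **The outcome is 42 factual items (14 + 11 + 17).** A participant cannot please an interviewer with a correct answer that he or she does not know. This largely stands, and it leaves prompting as the main route.
- **Training and restricted data access are safeguards.** They help in part. The text does not say that training covers prompting, and being unable to see submitted data has no bearing on the conduct of a live interview.
- **The fellow computes scores from recorded ticks.** This stands: no discretion in that step is apparent.
- **An effect lasting 12 months after one showing is speculative.** This stands as a reason to put most weight on the immediate test.
- **Swapping interviewers masks nobody.** This stands, since allocation is by village. Separating teacher from tester is a smaller aim than masking.

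A reader might also infer something from the fieldwork order: "The survey will start in Migoli, then Izazi, and then continue to the control villages". The inference would be that interviewers gain practice between the two groups' baselines, so that learning falls in group 1's change alone. The documents do not support this. Control baselines are also followed by later rounds with more practised interviewers, training and a pilot come first, and practice could make interviewers either stricter or more lenient.

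**Conclusion.** The point holds as a risk that the plan leaves open. Delivery and outcome interviewing are not separated, and the resulting bias may be differential, mainly in group 1 after exposure and most plausibly at the immediate test, in favour of the intervention. This rests on two assumptions: that some participants would in practice be tested by the person who taught them, and that prompting is possible with ticked items. The questionnaire itself is not in the text, so the second cannot be checked item by item.

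The size cannot be estimated. It may be tempting to suppose an interviewer effect of so many items and set it against the planned gain of 7 items (28 − 21), but nothing in the documents supports any particular number.

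Two further readings go too far. One is that bias will certainly enter and will touch group 1 only: the same unmasked team also interviews at baseline and in the control villages. The other is that interviewer effects could never be examined later because Table 1 lists no interviewer code: the documents do not say whether a submission can be traced to the enumerator's user account.

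The change is worth making because it is cheap and must be settled before data collection. The gap does not by itself invalidate the design.

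**What to change.** In Recruitment and participants and in Study tools, state that:

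1. Whoever showed a participant the videos does not administer that participant's 3-, 6- or 12-month questionnaire.
2. The same applies to the immediate questionnaire wherever two team members are present. NIMR enumerators, or SUA enumerators exchanging participants, can do this.
3. The fellow does no post-exposure outcome interviews in group 1.
4. Each interviewer works in both intervention and control villages, so that general interviewer tendencies are shared by the two groups.
5. The KoboCollect form in Table 1 carries an interviewer code, so that the planned multilevel models can examine interviewer effects.

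**Cost.** Some field scheduling, one form field and less flexibility in the immediate round. No extra staff are needed where existing interviewers can be reassigned. Team sizes are not given, and the Budget section mentions only transport from NIMR, so NIMR interviewing capacity is unknown; exchanges among SUA enumerators do not depend on it. Interviewers will still know which group a village belongs to, so the change reduces the risk without removing it.
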